The impact of BIIB092 on brain volumes, as determined by MRI in the regions mentioned above, will be evaluated relative to the change from baseline at Week 52 in the BIIB092-treated participants to that of the placebo-treated participants.

Tertiary objectives and endpoints are listed in Section 4.

Extension Objective(s) The primary objective of the open-label extension period is to assess the long-term safety and tolerability of BIIB092 in participants with PSP based on the numbers and percentages of deaths and of participants with SAEs and AEs. The secondary objective is to assess the long-term efficacy of BIIB092 in these participants based on clinical and health-outcomes measures.

Study Design: Randomized, double-blind, placebo-controlled, parallel-group study with an open-label extension period.

This study includes an optional substudy to measure quantitative movement assessments (QMAs) using wearable sensors. The QMAs will measure gait, postural instability, motor function, and falls in a subset of study participants participating in the long-term extension period.

Study Location: Approximately 98 sites are planned globally.

CONFIDENTIAL

The information contained herein may not be used, disclosed, or published without the written consent of Biogen MA Inc.

Number of Planned Participants: Approximately 459 participants will be randomly assigned, in a 2:1 ratio, to receive BIIB092 or placebo (306 participants in the BIIB092 treatment group and 153 in the placebo group).

Anticipating a dropout rate of approximately 25% (based on previous clinical studies in participants with PSP), approximately 345 participants (230 participants in the BIIB092 treatment group and 115 participants in the placebo group) are expected to complete the study through Week 52. Using a two-sided, two-sample t-test, with an alpha level set at 0.05, this sample size will provide 80% power to detect a difference of 3.2 points in the change in PSPRS total score from baseline to Week 52 for BIIB092 relative to placebo, assuming a common standard deviation of 9.95 in the change in PSPRS total score from baseline to Week 52.

Study Population: This study will be conducted in male and female participants with probable or possible PSP.

Women of childbearing potential (WOCBP) and sexually active fertile men with partners who are WOCBP must use highly effective birth control in Study 251PP301.

Detailed criteria are described in Section 6.

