3.3. Benefit/Risk Assessment

The benefit/risk profile of BIIB092 in nonclinical studies, the SAD study in NHVs (Study CN002001), and the MAD study and its associated open-label extension study (Studies CN002003 and 251PP201, respectively) supports further evaluation of the safety, tolerability, immunogenicity, PK, PD response, and clinical efficacy of BIIB092 in participants with PSP.

BIIB092 is a humanized IgG4 isotype antibody that is considered to have a low potential for immunogenicity in humans based on nonclinical studies. There were no adverse effects noted at any dose tested in the pivotal toxicity studies in monkeys. Nonclinical findings were limited to decreases in CSF unbound N-terminal tau consistent with the intended pharmacology of BIIB092. In completed clinical study CN002001, there was no consistent trend showing a potential effect of anti-drug antibody (ADA) on the PK of BIIB092. In completed clinical study CN002003, there was no apparent dose-related trend in the number of subjects with positive immunogenicity results post-treatment.

Studies evaluating the potential for reproductive and developmental toxicity have not been performed for BIIB092.

As of 25 November 2018, an estimated 486 participants have been exposed to BIIB092 across all completed (Studies CN002001 and CN002003) and ongoing clinical studies (Studies 251PP201, 251PP301, and 251AD201). Based on safety data from a completed Phase 1 study in healthy volunteers (Study CN002001) and a completed Phase 1B study in participants with PSP (Study CN002003), the benefit/risk profile of BIIB092 was favorable to support further clinical development.

There is no information available about possible interaction of BIIB092 with other drugs, although no PK interactions are anticipated.

More detailed information about the known and expected benefits and risks and reasonably anticipated AEs of BIIB092 may be found in the Investigator's Brochure. However, because BIIB092 is an experimental agent, it is possible that unforeseen, unknown, or unanticipated reactions may occur.

CONFIDENTIAL

The information contained herein may not be used, disclosed, or published without the written consent of Biogen MA Inc.

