6.1.3. Age and Reproductive Status

1. Males and females, ages 41 to 86 years, inclusive.
2. Women of childbearing potential (WOCBP) must have a negative serum or urine pregnancy test (minimum sensitivity 25 IU/L or equivalent units of human chorionic gonadotrophin) within 24 hours prior to the start of study treatment.
3. Women must not be breastfeeding
4. WOCBP must agree to follow instructions for method(s) of contraception for the duration of treatment with study treatment(s) BIIB092 plus 5 half-lives of study treatment BIIB092 plus 30 days (duration of ovulatory cycle) for a total of 155 days post-treatment completion.
5. Males who are sexually active with WOCBP must agree to follow instructions for method(s) of contraception ([Appendix 4](#)) for the duration of treatment with study treatment(s) BIIB092 plus 5 half-lives of the study treatment plus 90 days (duration of sperm turnover) for a total of 215 days post-treatment completion. In addition, male participants must be willing to refrain from sperm donation during this time.
6. Azoospermic males are exempt from contraceptive requirements. WOCBP who are continuously not heterosexually active are also exempt from contraceptive requirements and still must undergo pregnancy testing as described in this section.

Investigators shall counsel WOCBP, and male participants who are sexually active with WOCBP, on the importance of pregnancy prevention and the implications of an unexpected pregnancy. Investigators shall advise on the use of highly effective methods of contraception ([Appendix 4](#)).

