10.5. Pregnancy

Participants should not become pregnant or impregnate their partners for the duration of treatment with study treatment(s) BIIB092 plus 5 half-lives of study treatment BIIB092 plus 30 days for females (duration of ovulatory cycle) or 90 days for males (duration of sperm turnover) for a total of 155 days or 215 days for females and males, respectively. If a female participant becomes pregnant, study treatment must be discontinued immediately.

The Investigator must report a pregnancy occurring in a female participant by faxing or emailing the appropriate form to Biogen within 24 hours of the site staff becoming aware of the pregnancy. Refer to the Study Contact List for complete contact information. The Investigator or site staff must report the outcome of the pregnancy to Biogen. A pregnancy is not considered an AE and should not be recorded on the AE CRF.

Congenital abnormalities and birth defects in the offspring of male or female participants should be reported as an SAE if conception occurred during the study treatment period.

CONFIDENTIAL

The information contained herein may not be used, disclosed, or published without the written consent of Biogen MA Inc.

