- b Hormonal contraception may be susceptible to interaction with the study treatment, which may reduce the efficacy of the contraceptive method. Hormonal contraception is permissible only when there is sufficient evidence that the IMP and other study medications will not alter hormonal exposures such that contraception would be ineffective or result in increased exposures that could be potentially hazardous. In this case, alternative methods of contraception should be utilized.
- c Intrauterine devices and intrauterine hormone releasing systems are acceptable methods of contraception in the absence of definitive drug interaction studies when hormone exposures from intrauterine devices do not alter contraception effectiveness.

Unacceptable Methods of Contraception

- Periodic abstinence (calendar, symptothermal, post-ovulation methods)
- Withdrawal (coitus interruptus)
- Spermicide only
- Lactation amenorrhea method (LAM)

CONTRACEPTION GUIDANCE FOR MALE PARTICIPANTS WITH PARTNER(S) OF CHILD BEARING POTENTIAL.

Male participants with female partners of childbearing potential are eligible to participate if they agree to the following during the treatment and until the end of relevant systemic exposure.

- Inform any and all partner(s) of their participation in a clinical drug study and the need to comply with contraception instructions as directed by the Investigator.

[figure not shown]
No additional contraceptive measures are required to be used.

COLLECTION OF PREGNANCY INFORMATION

Guidance for collection of Pregnancy Information and outcome of pregnancy on the Pregnancy Notification and Outcome Form is provided in Section 10.5 and [Appendix 3](#).

[figure not shown]
CONFIDENTIAL

The information contained herein may not be used, disclosed, or published without the written consent of Biogen MA Inc.

[figure not shown]
CONFIDENTIAL

The information contained herein may not be used, disclosed, or published without the written consent of
Biogen MA Inc.

[figure not shown]
CONFIDENTIAL

[figure not shown]
The information contained herein may not be used, disclosed, or published without the written consent of
Biogen MA Inc.

[figure not shown]

CONFIDENTIAL

The information contained herein may not be used, disclosed, or published without the written consent of
Biogen MA Inc.

[figure not shown]

[figure not shown]
CONFIDENTIAL

The information contained herein may not be used, disclosed, or published without the written consent of
Biogen MA Inc.

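### The protocol gives conflicting contraception conditions, and an unclear duration, for non-azoospermic men who are sexually active with women of childbearing potential (WOCBP)

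*Protocol*

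**What the plan says.** Four places in the current protocol (Version 7) bear on the same men.

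- **Synopsis, Study Population:** "sexually active fertile men with partners who are WOCBP must use highly effective birth control in Study 251PP301".
- **Section 6.1.3, item 5 (inclusion criterion):** "Males who are sexually active with WOCBP must agree to follow instructions for method(s) of contraception", with a cross-reference to Appendix 4. The period is treatment "plus 5 half-lives of the study treatment plus 90 days (duration of sperm turnover) for a total of 215 days post-treatment completion". Sperm donation is ruled out over the same time. Item 6 exempts azoospermic men. The closing paragraph of 6.1.3 covers both WOCBP and men sexually active with them: "Investigators shall advise on the use of highly effective methods of contraception", again citing Appendix 4.
- **Section 10.5, Pregnancy:** participants are not to become pregnant or impregnate a partner during treatment and afterwards "for a total of 155 days or 215 days for females and males, respectively".
- **Appendix 4, guidance for male participants:** men with partners of childbearing potential may take part if they accept one printed duty. They must tell partners that they are in a drug study and that the Investigator's contraception instructions need to be followed. This applies through treatment and until systemic exposure is no longer relevant. The section then states "No additional contraceptive measures are required to be used".

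The only printed list of methods in Appendix 4 is headed for female participants and carries the female period of 155 days.

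**The concern.** Section 6.1.3 and the male section of Appendix 4 each state a condition of eligibility for the same men, and the two do not match. The first requires agreement to follow method instructions for a stated number of days. The second, as printed, requires partner notification for a period with no number and disclaims further measures. It also omits the sperm-donation restriction.

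Section 6.2.5 says participants must meet every eligibility criterion, and Section 9 allows no waivers. A criterion that can be read in two ways therefore invites avoidable deviations and uneven consent counselling. Partner protection is also involved, because Section 3.3 says: "Studies evaluating the potential for reproductive and developmental toxicity have not been performed for BIIB092". No endpoint, analysis or sample-size figure is affected.

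**Working it through.** **1. Reproduce the stated duration.** Section 6.1.3 gives the period for women as 5 half-lives "plus 30 days (duration of ovulatory cycle) for a total of 155 days post-treatment completion", and for men as 5 half-lives plus 90 days, in total 215.

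- From the female figure: 5 half-lives = 155 − 30 = 125 days, so one half-life = 125 / 5 = 25 days.
- From the male figure: 5 half-lives = 215 − 90 = 125 days, the same value.
- Male total: 125 + 90 = 215 days, which reproduces the protocol's figure. Section 10.5 agrees.

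The 215 days is internally sound. The problem lies in Appendix 4.

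**2. Set the passages side by side.**

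| Place | Measure for men | Period after treatment |
|---|---|---|
| Synopsis | Highly effective birth control | Not stated |
| 6.1.3, item 5 | Follow method instructions in Appendix 4; no sperm donation | 215 days |
| 6.1.3, closing paragraph | Investigator advises on highly effective methods, citing Appendix 4 | Not stated |
| 10.5 | Not to impregnate a partner; no method named | 215 days |
| Appendix 4, male section | Inform partners, including of Investigator-directed instructions; nothing additional required | End of relevant systemic exposure, undefined |

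**3. Follow the cross-reference.** A site applying item 5 goes to Appendix 4 for the instructions. The male section there refers to whatever the Investigator directs. The Investigator's own instruction in 6.1.3 is to advise using Appendix 4. The reference is circular, and in the printed text no step names a method for men.

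**4. Size the duration gap.** The Appendix term is undefined, so a figure needs an assumption.

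- If it means 5 half-lives: 125 days, and the gap is 215 − 125 = 90 days.
- If it also covers sperm turnover: 125 + 90 = 215 days, and the gap is 0.

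The range is 0 to 90 days. The conflict over measures does not depend on which reading is taken.

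**5. Number of men affected.** The documents do not give it. Inclusion covers ages 41 to 86, azoospermic men are exempt, and only men sexually active with WOCBP are concerned, so it may be a small part of the 459 planned participants.

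**The case against.** The strongest defence rests on the word *additional*. The Appendix bullet already mentions instructions directed by the Investigator, so the next sentence can be read as asking for nothing beyond those. Section 6.1.3 tells Investigators to advise highly effective methods and cites Appendix 4 as a whole, so a site could use the female list when counselling men. The Synopsis, 6.1.3 and 10.5 are mutually compatible, and Appendix 4 does not claim to override them. A graphic is also missing from the available text immediately before the quoted sentence, so what *additional* refers to cannot be seen with certainty.

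Much of this stands as a limit on the point. A reader might infer that the conflict is 215 days of contraception against none, or that Appendix 4 tells men they need no contraception. The documents do not support that: the Appendix sets a period, though an undefined one, and keeps the reference to Investigator-directed instructions. A reader might also infer that sites will apply opposite rules. The text supports only that the rules conflict and that sites may differ.

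The defence does not remove the point. Reading *additional* as beyond the Investigator's instructions leads back into the circular reference. The female list is not addressed to men, and its 155 days is not the male period. The undefined period stands in the printed lead-in to the male section, ahead of the missing graphic, and does not match 215 days on its face.

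**Conclusion.** The point holds as an internal inconsistency in current text. For non-azoospermic men sexually active with WOCBP, the Synopsis and Section 6.1.3 require contraception and 6.1.3 relies on Appendix 4 for the method. The male section of Appendix 4, as printed, supplies no method, disclaims additional measures and gives no number of days.

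The duration discrepancy is 0 to 90 days, on the assumption that relevant systemic exposure means something between 5 half-lives (125 days) and 5 half-lives plus sperm turnover (215 days). The conclusion about missing methods is limited to the printed text, because of the missing graphic. The consequence is possible variation between sites in counselling and screening, in an unknown number of men. It deserves correction because it sits in an eligibility rule that bears on partner safety, but it has no bearing on the trial's statistical results.

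**What to change.** Reconcile the Synopsis, Section 6.1.3 (item 5 and the counselling paragraph), Section 10.5 and the male section of Appendix 4, so that one statement covers both the measures and the duration for these men. Express the period either as a number of days or as a defined term, and make the cross-references end at that statement. Carry the same wording into consent and site counselling material, and notify sites.

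The clinical team decides which rule stands; this review proposes none. The cost is a wording change and site notification, with no effect on sample size, visit schedule or analysis.

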6.1.1. Signed Written Informed Consent

1. Participants, or a legally authorized representative (where local regulations and institutional practices permit), must have signed and dated an Institutional Review Board

CONFIDENTIAL

The information contained herein may not be used, disclosed, or published without the written consent of Biogen MA Inc.

(IRB)-/Independent Ethics Committee (IEC)-approved written informed consent form in accordance with regulatory and institutional guidelines. This must be obtained before the performance of any protocol-related procedures that are not part of normal participant care.

2. **The investigator must obtain consent consistent with the applicable legal, regulatory, and institutional policy requirements and specifically, taking into account the participant's state of disease progression and its impact on the participant's cognitive and motor abilities.**
3. **In the event that the study participant is unable to sign and date the informed consent form, a legally authorized representative, permitted to act on behalf of the participant in the context of this study, may provide consent on behalf of the participant.**

Rationale: Clarified the consent procedures for those participants who are able to give consent but who are unable to physically sign a consent form due to progression of disease.

Section 7, Treatment (Section 7.5, Preparation/Handling/Storage/Accountability)

Change: Language regarding the composition, preparation, handling, storage, and accountability of the BIIB092 study treatment was modified to refer to the Directions for Handling and Administration (DHA).

Now reads:

Study treatment will be manufactured, handled, and stored in accordance with applicable Good Manufacturing Practice.

BIIB092 is supplied as a liquid drug product in glass vials containing an extractable dose per the Directions for Handling and Administration (DHA). The contents of the BIIB092 label will be in accordance with all applicable regulatory requirements. BIIB092 should not be used after the expiration date.

BIIB092 must be stored refrigerated between 2°C and 8°C with protection from light. The placebo will be supplied locally and stored according to the packaging specifications. Study treatment not supplied by Biogen will be stored in accordance with the package insert.

~~The investigational product should be stored in a secure area according to local regulations. It is the responsibility of the Investigator to ensure that investigational product is only dispensed to study Participants. The investigational product must be dispensed only from official study sites by authorized personnel according to local regulations.~~

The product storage manager should ensure that the study treatment is stored in accordance with the environmental conditions (temperature, light, and humidity) as determined by ~~Biogen~~. **the**

CONFIDENTIAL

The information contained herein may not be used, disclosed, or published without the written consent of Biogen MA Inc.

DHA. If concerns regarding the quality or appearance of the study treatment arise, the study treatment should not be dispensed, and Biogen should be contacted immediately.

The study treatment should be stored in a secure area according to local regulations. It is the responsibility of the Investigator to ensure that study treatment is only dispensed to study participants. The study treatment must be dispensed only from official study sites by authorized personnel according to local regulations.

Study site staff should follow the DHA for specific instructions on the handling, preparation, administration, storage, and disposal of the study treatment. The DHA will also describe the masking of the IV bags of study treatment (both BIIB092 and placebo) to maintain the treatment blind. The DHA supersedes all other references (e.g., protocol or Investigator's Brochure).

Investigational product documentation (whether supplied by Biogen or not) must be maintained to ensure drug is accurately administered. This includes documentation of drug storage, administration and, as applicable, storage temperatures, reconstitution, and use of required processes (e.g., required diluents, administration sets).

~~Please refer to the current version of the Investigator Brochure and pharmacy manual for complete storage, handling, dispensing and infusion information for BIIB092.~~

~~Further guidance and information for final disposition of unused study treatment are provided in Appendix 2 and the pharmacy manual.~~

Rationale: Clarified that the DHA manual is to be followed as guidance for study site staff regarding handling, preparation, administration, storage, and disposal of the study treatment.

This change also affects Section 7, Table 6.

Section 8, Discontinuation Criteria

Change: This change identifies the discontinuation criteria for the study participants who discontinue study treatment but remain in the study and for the study participants who discontinue study treatment and withdraw early from the study.

Now reads:

8.1 Discontinuation From Study Treatment

Participants **MUST** discontinue ~~investigational product~~**study treatment** (and non-investigational ~~product~~**IP** at the discretion of the Investigator) for any of the following reasons:

- Participant's request to stop study treatment. Participants who ~~request to discontinue~~ study treatment ~~will~~**and remain enrolled** in the study ~~and must continue to~~**will** be followed for ~~protocol specified follow up~~ procedures. ~~The only exception to~~

CONFIDENTIAL

The information contained herein may not be used, disclosed, or published without the written consent of Biogen MA Inc.

~~this expected to complete scheduled safety and efficacy evaluations until the decision is when a participant specifically withdraws consent for any further contact with him/her or persons previously authorized by participant to provide this information made to withdraw from the study.~~

- Any clinical ~~adverse event (AE)~~, laboratory abnormality, or intercurrent illness which, in the opinion of the Investigator, indicates that continued participation in the study is not in the best interest of the participant
- Termination of the study by Biogen
- Loss of ability to freely provide consent through imprisonment or involuntary incarceration for treatment of either a psychiatric or physical (e.g., infectious disease) illness

~~Refer to the Schedule of Activities (Section 2) for data to be collected at the time of treatment discontinuation and follow up and for any further evaluations that can be completed.~~

In the case of pregnancy, the Investigator must immediately notify the Medical Monitor of this event. ~~In the event a normal healthy female participant becomes pregnant during a clinical trial, the~~ **and** study treatment must be discontinued immediately. In most cases, the study treatment will be permanently discontinued in an appropriate manner (e.g., dose tapering if necessary for participant safety). Please call the Medical Monitor within 24 hours of awareness of the pregnancy. If the Investigator determines a possible favorable benefit/risk ratio that warrants continuation of study treatment, a discussion between the Investigator and the Medical Monitor/designee must occur.

~~All participants who discontinue study treatment should comply with protocol specified follow up procedures as outlined in Section 2. The only exception to this requirement is when a participant withdraws consent for all study procedures including post treatment study follow up or loses the ability to consent freely (i.e., is imprisoned or involuntarily incarcerated for the treatment of either a psychiatric or physical illness).~~

If study treatment is discontinued prior to the participant's completion of the study, the reason for the discontinuation must be documented in the participant's medical records and entered on the appropriate ~~case report form (CRF)~~ page.

